15. SERIOUS ADVERSE EVENTS PROCEDURES

15.1 GENERAL DEFINITIONS

An adverse event (AE) is any untoward medical occurrence in a participant or clinical trial subject which does not necessarily have a causal relationship with this device/procedure and can include:

- any unintentional, unfavorable clinical sign or symptom
- any new illness or disease or the deterioration of existing disease or illness
- any clinically relevant deterioration in any laboratory assessments or clinical tests.

A Serious Adverse Event (SAE) is defined in general as an untoward (unfavourable) event which is:

- fatal or life-threatening*
- requires or prolongs hospitalisation
- is significantly or permanently disabling or incapacitating
- constitutes a congenital anomaly or a birth defect or
- may jeopardise the participant and may require medical or surgical intervention to prevent one of the outcomes listed above.

A SAE occurring to a participant which, in the opinion of the Chief Investigator, is Related and Unexpected will be reported to the main Research Ethics Committee (main REC).

The Research Ethics Service (RES) defines related and unexpected SAEs as follows:

- related to the study (i.e. they resulted from administration of any research procedures) and
- **unexpected** (i.e. not listed in the protocol as an expected occurrence)

15.2 OPERATIONAL DEFINITION AND PROCEDURES

15.2.1 EXPECTED AES / SAES - NOT REPORTABLE

It is expected that there will be minimal risks associated with the procedures of this study. For the purposes of this study, adverse events **related** to the study intervention will be collected and recorded in the CRFs and followed as appropriate. These adverse events may include (but does not represent an exhaustive list):

- Trauma from the impression procedure, examples would include:
 - o cuts from sharp impression trays
 - abrasions from impression trays
 - lips over stretched and cracked
- Vomiting from the impression procedure

^{*} The term life-threatening in the definition of a SAE refers to an event in which the participant was at risk of death at the time of the event; it does not refer to an event which hypothetically might have caused death if it was more severe.

- Allergic reaction from impression materials
- Allergic reaction to the acrylic impression tray

In recognition of this, only events fulfilling the definition of a **related** adverse event or serious adverse event will be collected in this study and reported to the main REC. All adverse events or serious adverse events **not** classified as 'related' will not be collected as part of this study.

15.2.2 RELATED AND UNEXPECTED SAES (RU SAES)

All Related and Unexpected SAEs occurring from the date of consent up to the last follow up appointment must be recorded on the Related Unexpected Serious Adverse Event Form, collated by the study team at DenTCRU and sent to the Sponsor within **one working day** of the research staff becoming aware of the event. The original form should also be posted to the DenTCRU in real time and a copy retained at site.

Email address for Reporting RU SAEs:

[contact]
Include 'URGENT - 3-D RU SAE' in the email subject

For each Related and Unexpected SAE the following information will be collected:

- full details in medical terms with a diagnosis, if possible
- date of Related and Unexpected SAE
- its duration (start and end dates; times, if applicable)
- action taken
- outcome

Any follow-up information should be emailed to DenTCRU at the address above as soon as it is available. Events will be followed up until the event has resolved or a final outcome has been reached.

All Related and Unexpected SAEs will be reviewed by the Chief Investigator and subject to expedited reporting to the Sponsor within one working day and to the main REC by the DenTCRU on behalf of the Chief Investigator within 15 days.

15.2.3 **DEATHS**

Deaths in the study population are not expected during the course of the study.

All deaths occurring from the date of consent up to the last assessment visit at the end of the Confirmation Period must be recorded and emailed to the DenTCRU within 7 days of the research staff becoming aware of the event and reported to the Sponsor. The original form should also be posted to DenTCRU in real time and a copy retained at site.

Email address for Reporting DEATHS:

[contact]

15.3 REPORTING

Safety issues will be reported to the Main REC in the annual progress report. An annual summary of all events will also be reported to the Sponsor. Expedited reporting of events (as detailed in Section 15.2.2) to the main REC and the Sponsor will be subject to current RES guidance, DenTCRU Standard Operating Procedures (SOPs) and Sponsor requirements.

15.4 RESPONSIBILITIES

15.4.1 CLINICAL CO-INVESTIGATORS / AUTHORISED PERSONNEL

- 1. Checking for SAEs when participants attend for study intervention.
- 2. Judgement in assessing:
 - Seriousness
 - Causality
 - Expectedness
- 3. To ensure all Related and Unexpected SAEs are recorded and reported to the DenTCRU within 24 hours of becoming aware and to provide further follow up information as soon as available.
- 4. To report Related and Unexpected SAEs to local committees in line with local arrangements.

15.4.2 CHIEF INVESTIGATOR (OR NOMINATED INDIVIDUAL IN CI'S ABSENCE)

- 1. Assign relatedness and expected nature of SAEs where it has not been possible to obtain assessment by authorised personnel.
- 2. Undertake SAE review.
- 3. Review all events assessed as Related and Unexpected in the opinion of authorised personnel. In the event of disagreement between the authorised personnel's assessment and the Chief Investigator, the authorised personnel's assessment may be upgraded or downgraded by the Chief Investigator prior to reporting to the Sponsor and through them to the main REC.

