5.2 OPERATIONAL STRUCTURE

Chief Investigator – The Chief Investigator leads on the design, conduct, co-ordination and management of the study.

Trial Management Group (TMG) - The TMG, comprising the Chief Investigator, Principal Investigators (PI), and Co-investigators will be assigned responsibility for the clinical set-up, on-going management, promotion of the study, and for the interpretation of results. Specifically the TMG will be responsible for (i) protocol completion, (ii) CRF development, (iii) obtaining approval from the main REC and regulatory authorities (iv) project initiation, (v) reporting of related unexpected serious adverse events, (vi) monitoring of screening, recruitment, treatment and follow-up procedures, (vii) auditing consent procedures, data collection, and database development.

Dental Translational Clinical Research Unit (DenTCRU) – The Research Programme Manager at DenTCRU will be responsible for the day-to-day running of the study including study administration, data management and safety reporting. The DenTCRU Lead Statistician will be responsible for all statistical analyses.

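### The Chief Investigator may downgrade a site's serious-event assessment before the Sponsor and REC are told; a disputed non-fatal event can then drop out of the safety reports, and the rule conflicts with Section 15.2.2

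*Protocol*

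**What the plan says.** Section 15.4.1 gives clinical staff at the site the judgement of seriousness, causality and expectedness. It also makes them responsible for prompt notification: "To ensure all Related and Unexpected SAEs are recorded and reported to the DenTCRU within 24 hours of becoming aware". They report such events to local committees too.

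Section 15.4.2 has the Chief Investigator review these events. If the two disagree, the site's assessment "may be upgraded or downgraded by the Chief Investigator prior to reporting to the Sponsor and through them to the main REC".

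Section 15.1 points the same way for the ethics committee: "A SAE occurring to a participant which, in the opinion of the Chief Investigator, is Related and Unexpected will be reported" to the main REC.

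Section 15.2.1 makes relatedness the condition for collection. Adverse events related "to the study intervention will be collected and recorded in the CRFs and followed as appropriate", while adverse and serious adverse events not judged related "will not be collected as part of this study".

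Section 15.2.2 sets the paperwork and a limit of one working day, counted from when research staff become aware. Each related and unexpected serious event "must be recorded on the Related Unexpected Serious Adverse Event Form, collated by the study team at DenTCRU and sent to the Sponsor within" that limit. The original form is posted to DenTCRU and a copy stays at the site. The Chief Investigator reviews these events, and DenTCRU reports to the main REC within 15 days. Section 15.2.3 has all deaths recorded and reported to the Sponsor, with no condition on relatedness.

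**The concern.** A chief investigator's review of causality is ordinary. Two features make it a weakness here. The review may lower the site's assessment before anyone outside the trial team is told, and an unrelated event has no other place in the safety data. In a trial that collects all serious events, a regraded event stays visible under another label. Here, regrading to unrelated takes it outside what the protocol collects.

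At stake is whether the Sponsor and the REC can judge a disputed case for themselves. Section 15.4.3 also asks DenTCRU to report any increase in related and unexpected serious events, and that signal depends on the same classification. Section 13.2 expects that pilot data may be combined with the later trial, so an event left out here could stay left out there.

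Separately, staff reading Sections 15.2.2 and 15.4.2 cannot tell whether the Sponsor hears before or after the Chief Investigator's review.

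**Working it through.** No arithmetic applies. The check follows one serious event, judged related and unexpected by the site, through Section 15.

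**1. What the site does.** It completes the dedicated form, notifies DenTCRU within 24 hours (15.4.1), posts the original, keeps a copy (15.2.2) and informs local committees (15.4.1). None of these steps is stated to wait for the Chief Investigator.

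**2. What a downgrade does.** There are three cases.

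- *Regraded from unexpected to expected.* Expedited reporting as a related and unexpected event falls away. The event is still related, so Section 15.2.1 still collects it in the CRFs.
- *Regraded from related to unrelated, non-fatal.* It no longer meets the REC reporting condition in 15.1, and 15.2.1 places it outside collection. The annual reports in 15.3 and 15.4.3 can draw only on what is collected, so nothing still requires the event to appear in them or in any safety summary. The form from step 1 still exists.
- *A death.* Section 15.2.3 has it recorded and reported to the Sponsor whatever its relatedness.

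Only the second case is exposed.

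**3. When the Sponsor is told.** Section 15.2.2 starts a limit of one working day when research staff become aware and mentions no regrading. Section 15.4.2 places regrading before the report to the Sponsor. The site's 24 hours to reach DenTCRU run from the same moment, so they can use up the Sponsor's working day and leave no time for a prior review. Section 15.2.2 then mentions Chief Investigator review and a one-working-day report to the Sponsor a second time, without giving a starting point. The two sections cannot both be followed in every case.

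**4. How the REC is told.** Section 15.4.2 goes through the Sponsor. Section 15.2.2 has DenTCRU report on the Chief Investigator's behalf, and the first item of 15.4.3 also gives DenTCRU expedited reporting to the REC.

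**5. Safeguards looked for.** No section requires both opinions to be recorded or forwarded, the more cautious view to prevail, or the site's assessment to remain in the reports after a downgrade. The management group in Section 5.2 ("The TMG, comprising the Chief Investigator, Principal Investigators (PI), and Co-investigators") is itself responsible for reporting these events, and no one outside the investigator team is given a role in settling a disagreement.

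**The case against.** The strongest reply is that the event is well documented whatever the Chief Investigator decides. The form reaches DenTCRU and stays on file at the site, local committees are told, sites keep copies of completed CRFs (Section 13), and source data may be verified (Section 16). Section 15.2.1 says unrelated events are not collected; it does not say that a form already submitted is withdrawn. On Section 15.2.2 alone, the Sponsor would have the form within a working day. Section 15.3 also makes expedited reporting subject to RES guidance, DenTCRU procedures and Sponsor requirements, which may deal with disagreements and are not available here.

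Much of this stands, and it rules out several stronger readings a reader might be tempted to draw:

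- *The event disappears without trace.* It does not, because the form remains at DenTCRU and at the site.
- *The Sponsor is certain not to see it.* That follows from 15.4.2, but 15.2.2 says otherwise. It is an unresolved conflict.
- *Nobody outside the investigators sees the event.* DenTCRU's Research Programme Manager handles safety reporting (Section 5.2), and local committees are informed.
- *The safety record is tilted in favour of the 3-D printed dentures.* Every participant wears both sets, and the listed expected events come from the impression stage, before the first randomisation. Nothing shows that a downgrade would favour one denture.
- *The reported rate would fall from 1/18 = 5.6% to zero.* This assumes exactly one event among the 18 participants, and that it is the one downgraded. The protocol gives no event rate.

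The reply does not show that the event must appear in any report after being regraded as unrelated. A form on file is not a report to the REC, and the protocol itself states no safeguard.

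**Conclusion.** The point holds in a limited form. Under Sections 15.1, 15.2.1 and 15.4.2 as written, one person's regrading can take a non-fatal serious event, judged related and unexpected by the site, out of the expedited report, the annual reports and the summarised safety data, although the source form survives. Regrading to expected does not do this, and deaths are covered separately. Sections 15.2.2 and 15.4.2 also contradict each other on when the Sponsor is told, and the sections differ on who reports to the REC.

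The size cannot be quantified: few such events are likely in a low-risk study, and safety comparison is not among the objectives. The weakness lies in the reporting rule, not in any efficacy result. The conclusion assumes that no external procedure cited in Section 15.3 overrides the protocol text; if one does, the protocol should say so. The change should be made because it protects safety reporting at almost no cost.

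**What to change.** Reconcile Sections 15.1, 15.2.1, 15.2.2, 15.4.2 and 15.4.3 together; changing 15.4.2 alone would leave 15.1 and the timing conflict in place.

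- **15.4.2:** the Chief Investigator may upgrade but not downgrade the site's assessment before reporting. Any disagreement is recorded, with both opinions.
- **15.1 and 15.2.2:** a serious event judged related and unexpected by either the site or the Chief Investigator is reported to the Sponsor and the main REC within the limits already in 15.2.2, with both opinions attached. State that the Sponsor's limit runs from staff awareness and does not wait for the Chief Investigator's review.
- **15.2.1:** a serious event once assessed by a site as related stays in the safety data and annual summaries whatever the later review concludes.
- **15.2.2, 15.4.2 and 15.4.3:** name one route to the REC, either DenTCRU directly or through the Sponsor, and use it throughout.

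The cost is a wording amendment and an occasional expedited report that the Chief Investigator would have thought unnecessary. No new data collection is needed, since the form already exists.

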15.4.3 DENTCRU

- 1. Expedited reporting of RU SAEs to the main REC and Sponsor within required timelines.
- 2. Preparing annual safety reports at least annually to the main REC on behalf of the Sponsor. Safety may be reported more frequently if appropriate.
- 3. Expedited reporting of other safety issues, including an increase in the rate of occurrence in severity of RU SAEs, to the main Sponsor and through them to the REC within required timelines.

16. DATA MONITORING

Data will be monitored for quality and completeness by a member of the study team at DenTCRU (University of Leeds). Missing data will be chased until it is received, confirmed as not available or the study is at analysis. DenTCRU/Sponsor will reserve the right to intermittently conduct source data verification exercises on a sample of participants, which will be carried out by authorised staff from DenTCRU/Sponsor.

16.1 CLINICAL GOVERNANCE ISSUES

To ensure responsibility and accountability for the overall quality of care received by participants during the study period, clinical governance issues pertaining to all aspects of routine management will be brought to the attention of the TMG and, where applicable, to the participating NHS Trust.

17. QUALITY ASSURANCE AND ETHICAL CONSIDERATIONS

17.1 QUALITY ASSURANCE

The study will be conducted in accordance with the principles of Good Clinical Practice, the UK Policy Framework for Health and Social Care Research and through adherence to DenTCRU/University of Leeds Standard Operating Procedures (SOPs).

17.2 ETHICAL CONSIDERATIONS

The study will be performed in accordance with the recommendations guiding physicians in biomedical research involving human subjects adopted by the 18th World Medical Assembly, Helsinki, Finland, 1964, amended at the 48th World Medical Association General Assembly, Somerset West, Republic of South Africa, October 1996. Informed written consent will be obtained from the participants prior to registration into the study. The right of a participant to refuse participation without giving reasons must be respected. The participant must remain free to withdraw at any time from the study without giving reasons and without prejudicing his/her further treatment. The study will be submitted to and approved by a main Research Ethics Committee (Main REC) prior to entering participants into the study. The DenTCRU (University of Leeds) will provide the Main REC with a copy of the final protocol, participant information sheets, consent forms and all other relevant study documentation.

18. CONFIDENTIALITY

All information collected during the course of the study will be kept strictly confidential. Information will be held securely on paper, electronically and digitally by the research sites. The research sites will comply with all aspects of the Data Protection Act as modified in 2018 and operationally this will include:

- Consent from participants to record personal details including name and date of birth.
- Participant name will be collected when a participant is registered into the study but all other data collection forms that are transferred to or from the DenTCRU (University

- of Leeds) will be coded with an individual participant study ID number and will include two patient identifiers, usually the participant's initials and date of birth.
- Appropriate storage, restricted access and disposal arrangements for participant personal and clinical details.
- Consent from participants for access to their healthcare records by responsible individuals from the research staff or from regulatory authorities, where it is relevant to study participation.
- Consent from participants for the data collected for the study to be used to evaluate safety and develop new research.
- Where central monitoring of source documents by DenTCRU (or copies of source documents) is required (such as denture scans), the participant's name must be obliterated by site before sending.
- Where anonymisation of documentation is required, sites are responsible for ensuring only the instructed identifiers are present before sending to DenTCRU.

If a participant withdraws consent from further intervention and / or further collection of data, all collected data will always be included in the final study analysis.

19. ARCHIVING

At the end of the study, data will be securely archived in line with the Sponsor's procedures for a minimum of 5 years. Data and documents held by the participating research sites will be archived on site. Following authorisation from the Sponsor, arrangements for confidential destruction will then be made.

20. STATEMENT OF INDEMNITY

This study is sponsored by The University of Leeds, which is responsible for the design and management of the research and will be liable for negligent harm caused by the design of the study. The NHS has a duty of care to participants treated, whether or not the patient is taking part in a clinical trial, and the NHS remains liable for clinical negligence and other negligent harm to participants under this duty of care.

As this is a clinician-led study there are no arrangements for no-fault compensation.

20.1 FUNDING

This study is funded by The Dunhill Medical Trust grant *RPGF1802\33: 3-D Printed Dentures; Development and assessment of cost-effective workflows to enhance clinical delivery.*

21. PUBLICATION POLICY

21.1 AUTHORSHIP AND ACKNOWLEDGEMENT

The success of the study depends upon the collaboration of all participants. For this reason, credit for the main results will be given to all those who have collaborated in the study, through authorship and by contribution. Uniform requirements for authorship for manuscripts submitted to medical journals will guide authorship decisions. These state that authorship credit should be based on the following ICMJE criteria:

- substantial contribution to the conception and design, or acquisition, analysis, or interpretation of data
- drafting the work or revising it critically for important intellectual content
- final approval of the version to be published
- agreement to be accountable for all aspects of the work

In light of this, the Chief Investigator, Co-Applicants and senior DenTCRU staff may be named as authors in any publication, and an appropriate first author agreed through discussion amongst the Trial Management Group (TMG) members. In addition, all collaborators will be listed as contributors for the main study publication, giving details of their roles in planning, conducting and reporting the study. The research team should be acknowledged in all publications, as should Dunhill Medical Trust (as detailed below). Other key individuals will be included as authors or contributors as appropriate and at the discretion of the TMG.

21.2 DATA RELEASE

To maintain the scientific integrity of the study, data will not be released prior to the first publication of the results of the primary endpoint analysis, either for study publication or oral presentation purposes, without the permission of the TMG.

Individual collaborators must not publish data concerning their participants which is directly relevant to the questions posed in the study until the main results of the study have been published, without the permission of the TMG.

21.3 PROCESSES FOR THE DRAFTING, REVIEW AND SUBMISSION OF ABSTRACTS AND MANUSCRIPTS

The agreed first author of abstracts is responsible for circulating these to the other members of the Trial Management Group (TMG) for review at least 15 days prior to the deadline for submission.

The agreed first author of manuscripts is responsible for ensuring:

- timely circulation of all drafts to all co-authors during manuscript development and prior to submission
- timely (and appropriate) circulation of reviewers' comments to all co-authors
- incorporation of comments into subsequent drafts
- communication with the TMG

The first author is responsible for submission of the publication and must keep the TMG and all authors informed of the abstract's or manuscript's status. On publication, the first author should send copies of the abstract or manuscript to the TMG, the Sponsor and to all coauthors, and ensure communication with The Dunhill Medical Trust.

